### **7.1 Treatment duration and modification**

### **7.2 Medical Device**

### 7.2.1 Medical device and it's characteristics:

P-STIM is a battery-operated micro-stimulation appliance weighing 5 grams designed as a disposable product for a single use. P-STIM is placed behind the patient's ear and connected to stimulation needles on the auricle. P-STIM offers regular therapy over several days. The appliance transmits low-frequency electric pulses to exposed nerve endings, which triggers the release of endorphins. The built-in microchip creates periods of stimulation and rest, each lasting approximately 3 hours. After a time it could feel as if the intensity of stimulation is decreasing. A decrease in the perceived intensity of stimulation may be subjective and have no bearing on the effectiveness of the therapy.

### 7.2.2 Manufacturer (Model or Type Number including software and accessories):

**Manufacturer:**

**Firma Biegler Medizinelektronik**

**Biegler GmbH**

**[name],**

**[name], AUSTRIA**

Appliance: Point stimulation appliance

Type description: P-STIM

Power supply: 3 x 1.4V batteries (Type AC 10E)

Output: (Load impedance range 1k-10k $\Omega$ ) max. 3.8V,

Impulse interval 1000ms, Impulse width 1ms, (1Hz / 1ms / bipolar), max possible total duration of treatment 4 x 24 hours

The amplitude of the output signal diminishes in proportion to battery voltage.

Protection level: IP20 | Type: B

Classification (in accordance with Directive 93/42 EEC): II a

Duty type: approx. 3h duty / 3h at rest (periodic duty)

Weight incl. battery: 5 g | Dimensions: 63 x 28 x 8 mm

Needle Dimensions: 0.4 mm width x 2 mm length

### 7.2.3 Installation and handling instructions

The appliance is splash-proof but not watertight. If desired, hair should be washed before therapy.

When showering, the appliance must not be allowed to come into direct contact with water.

Do not use P-STIM and accessories when package is damaged.

The sterile stimulation needles are only intended for SINGLE use.

Do not resterilise!

The re-use of single-use products represents a possible risk of infection for the patient or user. Any product contamination can damage the health of the patient and lead to illness or death.

The Multi-Point stylus, the ring applicator and the stimulation needles are to be used with the P-STIM only and for no other purpose. If a needle is fitted more than three times with the same cap, or the cap is damaged mechanically or the red release button on the Multi-Point is pressed too early, the needle may become detached prematurely. Never hold the Multi-Point against the face or eyes with a needle attached. If the appliance and/or needles become detached, they must not be

refastened by the patient under any circumstances. The patient should visit his doctor as soon as possible in order to have the puncture points disinfected.

When removing the appliance it is important that care be taken to avoid contact with the needles.

The needles can be separated from the P-STIM appliance by carefully cutting through the connection leads. It is important that all contaminated tips or sharp objects in medical use are handled with extreme care (Information taken from P-STIM® User Manual).

#### **Premature permanent discontinuation due to an adverse event**

If the reason for premature permanent discontinuation of clinical investigation is an AE, the patient should have a "Premature EOS" visit with all the assessments performed before the discontinuation of the treatment with the medical device, whenever possible.

#### **Premature permanent discontinuation due to another reason than adverse event**

If the reason for premature permanent discontinuation of clinical investigation is not an AE, the patient should be withdrawn (withdrawal of consent) and have the EOS visit with all the assessments performed before the medical device discontinuation, whenever possible.

#### **7.2.4 Concomitant medication**

The well-being of the patient has the first priority therefore this clinical investigation allows all concomitant medications as long they are stable since over 1 months.

#### **7.2.5 Interactions, reverse reactions and side effect of the medical device:**

-Use of the appliance in the vicinity (approx. 1m) of short-wave, microwave or RF appliances can be the cause of interference and must therefore be avoided. (Tested in accordance with EN 60601-1-2.)

#### **Contraindications**

- Use of cardiac pacemakers because no clinical data are available
- Hemophilia
- Psoriasis vulgaris, an intact skin surface is essential for the use of P-STIM

#### **7.3 Randomization and stratification:**

After the screening visit, patients will be randomized into one of the following treatment groups: group V (Verum electrical vagus stimulation) or group P (placebo).

#### **7.4 Blinding**

Patients will receive a dummy of the medical device, which looks like the original. Patient and investigator are blinded. A study nurse controls the list with treatment numbers and treatment groups (placebo or verum).

**Unblinding -procedure at the end of the clinical investigation:**

At the end of study, codes will be unblinded and data will be analyzed.

**7.5 Benefit and risk assessment**

A recent safety study summarizes the adverse events of acupuncture. Wheway J et al analyzed 325 incidents during acupuncture treatment. Adverse events reported include retained needles (31%), dizziness (30%), loss of consciousness/unresponsive (19%), falls (4%), Bruising or soreness at needle site (2%), Pneumothorax (1%) and other adverse reactions (12%). The majority (95%) of the incidents were categorised as low or no harm [Wheway J et al, 2012]. On auricular acupuncture in particular we found no safety data. We expect a similar safety profile to body acupuncture.

**7.6 Clinical investigation procedures**

**7.6.1 General rules for clinical investigation procedures**

- All clinical investigation measures like blood sampling and measurements (vital parameters, ECG, etc.) have to be documented with date (dd:mm:yyyy).
- In case several clinical investigation procedures are scheduled at the same time point, there is no specific sequence that should be followed.
- The dates of all procedures should be according to the CIP. The time margins mentioned in the clinical investigation flow chart are admissible. If for any reason, a clinical investigation procedure is not performed within scheduled margins a CIP deviation should be noted, and the procedure should be performed as soon as possible or as adequate.
- If it is necessary for organizational reasons, it is admissible to perform procedures which are scheduled for one visit at two different time points. Allowed time margins should thereby not be exceeded.

**7.6.2 Screening investigation**

**BEFORE TREATMENT RANDOMISATION V-1**

*(Study Day 1)*

After signing the informed consent all patients will be screened according to exclusion and inclusion criteria. Patients will be investigated as follows:

- Prior medical history will be assessed.
- ECG (Electrocardiogram) will be performed
- blood pressure
- blood samples will be collected ( TNF $\alpha$ , IL6, CRP and NT-proBNP levels will be assessed).
- base line LVEF (not older than 14 days) assessed by transthoracal echocardiography
- 6 min walk test
- quality of life assessment with SF 36
- Assessment of NYHA classification (see table 2)

**BASE LINE VISIT V0**

*(Study Day 7)*

After randomization to verum or placebo group

-treatment according to randomizations: patients receive dummy or original medical device.  
Acupuncture will be performed in the concha of the ear. Patients will be instructed how to use device (eg during showering, if the patch removes etc). Device is removed by patient after 4 days.

#### V1-V4

(Study Day 14, 21, 28, 35)

Patients receive new device, possible adverse events can be assessed, possible complications/questions can be discussed.

Day 21: 6 minutes walk test will be performed again.

#### End of Study Visit V5

(Study Day 63)

- ECG (Electrocardiogram) will be performed
- blood pressure
- blood samples will be collected ( TNF $\alpha$ , IL6, CRP and NT-proBNP levels will be assessed).
- LVEF (not older than 14 days) assessed by transthoracal echocardiography
- 6 min walk test
- quality of life assessment with SF 36
- Assessment of NYHA classification

Class	Patient Symptoms
Class I (Mild)	No limitation of physical activity. Ordinary physical activity does not cause undue fatigue, palpitation, or dyspnea (shortness of breath).
Class II (Mild)	Slight limitation of physical activity. Comfortable at rest, but ordinary physical activity results in fatigue, palpitation, or dyspnea.
Class III (Moderate)	Marked limitation of physical activity. Comfortable at rest, but less than ordinary activity causes fatigue, palpitation, or dyspnea.
Class IV (Severe)	Unable to carry out any physical activity without discomfort. Symptoms of cardiac insufficiency at rest. If any physical activity is undertaken, discomfort is increased.

Table 2: New York Heart Association (NYHA) Classification

## 8. SAFETY DEFINITIONS AND REPORTING REQUIREMENTS

### 8.1 Adverse events (AEs)/Adverse device effects (ADEs)

#### 8.1.1 Definition of adverse event and adverse device effect

An AE/ADE is any adverse change from the subject's baseline condition, i.e. any unfavorable and unintended sign including an abnormal laboratory finding, symptom or disease which is considered to be clinically relevant by the physician that occurs during the course of the, whether or not considered related to the medical device.

Adverse event /ADE include:

- Exacerbation of a pre-existing disease.
- Increase in frequency or intensity of a pre-existing episodic disease or medical condition.
- Disease or medical condition detected or diagnosed after treatment with the medical device even though it may have been present prior to the start of the clinical investigation.
- Continuous persistent disease or symptoms present at baseline that worsen following the start of the clinical investigation.
- Lack of efficacy in the acute treatment of a life-threatening disease.
- Events considered by the investigator to be related to clinical investigation-mandated procedures.
- Abnormal assessments, e.g., ECG and physical examination findings, must be reported as AEs/ADEs if they represent a clinically significant finding that was not present at baseline or worsened during the course of the clinical investigation.
- Laboratory test abnormalities must be reported as AEs/ADEs if they represent a clinically significant finding, symptomatic or not, which was not present at baseline or worsened during the course of the clinical investigation lead to interruption or permanent discontinuation of medical device.

Adverse events do not include:

- Pre-planned interventions or occurrence of endpoints specified in the CIP are not considered AEs/ADEs, if not defined otherwise.
- Medical or surgical procedure, e.g. surgery, endoscopy, tooth extraction, transfusion. However, the event leading to the procedure is an AE. If this event is serious, the procedure must be described in the SAE/SADE narrative.
- Pre-existing disease or medical condition that does not worsen.
- Situations in which an adverse change did not occur, e.g., hospitalizations for cosmetic elective surgery or for social and/or convenience reasons.
- Misuse of either medical device or concomitant medication without any signs or symptoms. However, misuse must be mentioned in the Medical Device Inventory/ Treatment Log.

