## 2. SYNOPSIS OF THE CLINICAL INVESTIGATION

TITLE	Clinical Outcome of Electrical Auricular Vagal Stimulation in Patients with Stable Symptomatic Chronic Heart Failure -a Pilot Study					
ACRONYM	(abbreviated title)					
NAME OF DEVICE	Dev1					
DESCRIPTION OF THE PROCEDURES	P-Stim® is an investigational device intended to deliver electrical auricular acupuncture in individuals suffering from heart failure. The device system is to be used only in accordance with the approved Investigational Plan on subjects who have signed an informed consent form. Device use is limited to the approved study investigators.					
OBJECTIVES	
In this study the effects of electrical auricular acupuncture on symptomatic chronic heart failure will be assessed.
 
Primary Objective:
 

- Six-minute walk test

 
Secondary Objective:
 

- Left ventricular ejection fraction (LVEF)

- New York Heart Association (NYHA) classification

- In addition the patient's quality of life (regarding to different areas in daily life, mobility etc.) will be assessed by a quality of life questionnaire (SF 36)

- Adverse events of acupuncture will be recorded

- Inflammatory cytokines TNF <math>\alpha</math>, IL6, NT-proBNP, CRP, will be collected to measure a possible influence of electrical auricular acupuncture on inflammation

- Ventricular and/or atrial arrhythmia documented in a subgroup of patients with implanted cardiac rhythm management devices.

					
TYPE OF THE INVESTIGATION	Prospective, single center, randomized, parallel group, double-blind, placebo-controlled					
PERIOD OF ENROLMENT	First patient First visit	1.1.20 13	Last patient First visit	31.12. 2013	Last patient Last visit	28.2.10 14
CENTER(S) / COUNTRY(IES)	1 center, Medical University Vienna, Austria					
PATIENTS / GROUPS	40 patients in 2 groups 20 patients per group Randomization ratio 1:1, stratification gender					
INCLUSION CRITERIA	

- Stable symptomatic chronic heart failure, defined by:

- NYHA Classification II-III

- Optimal medical treatment (ESC guidelines 2012) for at least 1 month

					

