### **5.2 Secondary Objectives (Hypothesis)**

- Quality of Life assessed by SF 36
- adverse events of electrical auricular vagal stimulation will be recorded
- blood levels of inflammatory cytokines TNF  $\alpha$ , IL6, NT-proBNP, CRP
- LVEF (assessed by transthoracal echocardiography)
- NYHA (New York Heart Association) classification

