#### **Mild**

Event may be noticeable to subject; does not influence daily activities; the AE /ADE resolves spontaneously or may require minimal therapeutic intervention;

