### 8.4 Relationship to medical device

For alls, the investigator will assess the causal relationship between the medical device and the AE/ADE using his/her clinical expertise and judgment according to the following algorithm that best fits the circumstances of the AE/ADE:

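### Section 8.1.1 counts a symptom as an adverse event only if the physician finds it clinically relevant, with no criteria, so mild device effects can go unrecorded

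*Combined protocol and SAP*

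**What the plan says.** - **Definition.** Section 8.1.1 defines AE and ADE in one sentence. It covers an unfavourable sign, "symptom or disease which is considered to be clinically relevant by the physician", and applies "whether or not considered related to the medical device". Nothing says how relevance is to be judged. Later bullets in the same section set separate clinical-significance tests for ECG and examination findings and for laboratory abnormalities.
- **Severity.** Section 8.3 opens its mild grade with "Event may be noticeable to subject; does not influence daily activities". The grade covers events that resolve on their own or need minimal treatment.
- **Causality.** Under section 8.4, "the investigator will assess the causal relationship between the medical device and the AE/ADE using his/her clinical expertise and judgment", on three levels: unrelated, possibly related, definitely related. Section 8.5 makes that rating a field in the case report form, and 8.5.1 requires device-relatedness in serious-event reports.
- **Objective.** The synopsis lists among the secondary objectives "Adverse events of acupuncture will be recorded". Section 5.2 (Secondary Objectives) has "adverse events of electrical auricular vagal stimulation will be recorded".
- **Prior knowledge.** Section 7.5 reports that no safety data specific to auricular acupuncture were found, and expects a profile like that of body acupuncture.

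**The concern.** Clinical relevance is normally a matter of grading: the event is recorded, then rated. Here it decides whether the event exists. The screen acts before every other safety step, so what it removes cannot be recovered later by grading, causality review, monitoring or analysis.

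This matters because of what a 40-patient pilot can show about safety. It will say little about rare serious harm. It can show which mild effects are common when needles and a stimulator are worn on the ear for days at a time. Those are the events a physician is most likely to call unimportant. With no criteria, two physicians may also decide the same complaint differently, so the recorded count would depend partly on who saw the patient.

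**Working it through.** The plan states no figure on this point, so the check is mainly a comparison of sections.

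1. **What the clause governs.** It may qualify the whole list (sign, symptom, disease) or only the last two items. Symptoms are filtered on either reading.
2. **Whether it is needed.** Trivial test results are already kept out by the clinical-significance tests in the ECG/examination and laboratory bullets of 8.1.1. The main added effect of the general clause is therefore on what patients report, such as soreness or dizziness.
3. **Whether another part of 8.1.1 brings the events back.** One inclusion bullet covers events related to investigation-mandated procedures and carries no relevance condition. It does not clearly cover device effects, because section 8.2.2, writing of serious events, describes such procedures as excluding administration of the device.
4. **Whether a later step brings them back.** Sections 8.3, 8.4, 8.5 and 8.5.1 all start from an event already accepted as an AE or ADE. None looks at a symptom that was screened out.
5. **Whether ADEs can be told apart.** The shared sentence in 8.1.1 does not separate them. The causality field in 8.4 and 8.5 does: an ADE can be derived as an AE rated possibly or definitely related. Only a symptom that fails the relevance test escapes that field.

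**Illustration of the mechanism only.** Let p be the true per-patient risk of a mild effect and c the share of such effects judged relevant. Both are assumptions; the documents give neither. With the planned 20 patients in a group, the chance of recording at least one case is 1 − (1 − pc)^20, and the expected number of recorded cases is 20pc.

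| p | c = 100% | c = 50% | c = 25% |
|---|---|---|---|
| 10% | 88% (2 expected) | 64% (1) | 40% (0.5) |
| 20% | 99% (4) | 88% (2) | 64% (1) |
| 30% | 99.9% (6) | 96% (3) | 79% (1.5) |

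For example, with p = 10% and c = 50%, 1 − 0.95^20 = 0.64. The table shows how a filter of this kind works in a group of 20. It is not evidence of how strong the filter would be in this trial.

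**The case against.** The strongest reply is that the plan plainly means to record mild events. Section 8.3 gives them a grade, the list in 8.1.1 of what is not an adverse event does not exclude them, and mild is not the same as irrelevant, since the mild grade includes events that need minimal treatment. This stands in part. The filter can drop some mild events; nothing says that it removes that class, and a reader should not infer that it does. But the existence of a mild grade does not help a symptom that was never admitted.

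Three stronger readings are tempting, and the documents support none of them.

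- **That device effects cannot be separated from other events.** The shared definition invites this, but the causality rating and its field in 8.4 and 8.5 refute it.
- **That up to 95% of expected events could be filtered out**, because section 7.5 says "The majority (95%) of the incidents were categorised as low or no harm". That figure grades 325 reported acupuncture incidents by harm. It is neither a per-patient rate nor a measure of clinical relevance. The listed categories add to 31 + 30 + 19 + 4 + 2 + 1 + 12 = 99%, so they look exclusive. About 5% of incidents lie outside low or no harm, yet loss of consciousness or unresponsiveness makes up 19%. At least 19 − 5 = 14 percentage points of the 95% must then be that category, which a physician would hardly dismiss. Bruising or soreness is only 2%.
- **That the filter biases the comparison between arms.** Section 7.4 blinds patient and investigator, so the judgement is planned to be made blind in both groups. Whether the blind holds is a separate question.

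It can also be said that loose collection is as likely a cause of under-recording. In section 7.6.2 the wording for V1-V4 only allows adverse events to be assessed, and the V5 list has no adverse event item. That is fair, and correcting the definition does not cure it. It is an additional weakness, not a defence of the clause.

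**Conclusion.** The point holds as a defect of wording with a practical consequence. Followed as written, section 8.1.1 lets a physician leave a mild symptom out of the record without any stated criterion, and no other section reverses that. The conclusion assumes only that the definition is applied as it reads. It does not show that under-recording will happen, and its extent cannot be estimated from the documents.

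The weight is modest. Nothing changes in the sample size, the significance level or the analysis of the walk test. The change is still worth making before enrolment, because events left out cannot be restored afterwards and adverse events are a stated objective in a setting where the plan found no specific safety data. The lack of a separate ADE definition is a minor point of clarity.

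**What to change.** 1. In the general sentence of 8.1.1, delete the clause that makes the physician's view of clinical relevance a condition. Keep the clinical-significance test where it already stands, in the ECG/examination and laboratory bullets, and say that those bullets govern test findings so that the general sentence does not readmit trivial results.
2. As a minor clarification in 8.1.1 and 8.2, state that an ADE is an AE rated possibly or definitely related to the device, and that a SADE is a serious ADE. Both follow from fields already in the case report form.

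The cost is a few sentences of text, a few more mild-event lines in the form, and an adverse event table that looks less favourable. No extra patients, visits or measurements are needed.

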### 8.2 Serious adverse events (SAE)/Serious adverse device effects (SADEs)

A Serious Adverse Event (SAE)/Serious adverse device effect is defined as any AE/ADE fulfilling at least one of the following criteria:

- leads to a death,
- leads to a serious deterioration in the health of the subject that
  - 1) resulted in a life-threatening illness or injury,
  - 2) resulted in a permanent impairment of a body structure or a body function,
  - 3) required in-patient hospitalization or prolongation of existing hospitalization,
  - 4) resulted in medical or surgical intervention to prevent permanent impairment to body structure or a body function.
- leads to foetal distress, foetal death or a congenital abnormality or birth defect.
- is an important medical event that may not immediately result in death, be life-threatening, or require hospitalization but may be considered as SAEs/SADEs when, based upon appropriate medical judgment, it may jeopardize the subject and may require medical or surgical intervention to prevent one of the outcomes listed in the definitions above.
- shows the occurrence of a malignant tumor (§3 (16) MPG).

Life-threatening refers to an event in which the subject was at risk of death at the time of the event. It does not refer to an event that hypothetically might have caused death if it were more severe.

